8.6. Physical Examinations

Physical examinations will be performed at the time points detailed in Table 3 of the study protocol. Physical examinations will not be summarized. Any finding will be listed.

Weight, height and BMI will be assessed as a part of the vital signs (Section 8.7).

8.7. Vital Signs

Vital signs (blood pressure [BP; systolic/diastolic], respiratory rate, body temperature, and pulse) will be measured at the time points detailed in Table 3 of the study protocol.

Vital signs (supine or semi erect/seated) values and changes from baseline to each visit will be summarized using descriptive statistics. The last assessment will be defined as in Section 4.4.

Orthostatic systolic and diastolic BP and pulse will be calculated as supine or semi erect/seated measurement minus standing measurement and values and changes from baseline to each visit will be summarized using descriptive statistics. Any cases where standing measurements were taken less than 3 minutes after the supine or semi erect/seated measurement will be excluded from the analysis.

Orthostatic hypotension (determined by BP measurements only; positive value in case of abnormality) is defined as having either a ≥ 20 mmHg reduction from supine to standing position in systolic blood pressure (SBP) or ≥ 10 -mmHg reduction from supine to standing position in diastolic blood pressure (DBP) or both. Orthostatic tachycardia is defined as pulse increase ≥ 20 beats per minute (bpm) from supine to standing position.

Summaries of potentially clinically significant abnormal values will include all post-baseline values (including scheduled, unscheduled, and withdrawal visits). The incidence of potentially

clinically significant abnormal values will be summarized using descriptive statistics with the criteria specified in [Table 6](#).

[Table 6](#) specifies the criteria for identifying vital signs as potentially clinically significant abnormal values.

Table 6: Criteria for Potentially Clinically Significant Vital Signs

Vital Sign (unit)	Age	Potentially Clinically Significant Low Criterion value	Potentially Clinically Significant High Criterion value
SBP (supine/ seated/ semi-erect) (mmHg)	6-12	Value ≤ 70 and ≥ 20 decrease from baseline	Value ≥ 120 and ≥ 20 increase from baseline
	13-18	Value ≤ 90 and ≥ 20 decrease from baseline	Value ≥ 135 and ≥ 20 increase from baseline
DBP (supine/ seated/ semi-erect) (mmHg)	6-12	Value ≤ 40 and ≥ 15 decrease from baseline	Value ≥ 80 and ≥ 15 increase from baseline
	13-18	Value ≤ 50 and ≥ 15 decrease from baseline	Value ≥ 90 and ≥ 15 increase from baseline
Pulse rate (supine/ seated/ semi-erect) (bpm)	6-10	Value ≤ 60 and ≥ 15 decrease from baseline	Value ≥ 135 and ≥ 15 increase from baseline
	11-18	Value ≤ 50 and ≥ 15 decrease from baseline	Value ≥ 120 and ≥ 15 increase from baseline
SBP orthostatic criteria (mmHg)	~	≥ 20 decrease from supine to standing position	NA
DBP orthostatic criteria (mmHg)	~	≥ 10 decrease from supine to standing position	NA
Pulse rate orthostatic criteria (bpm)	~	NA	≥ 20 increase from supine to standing position
Temperature ($^{\circ}$ C)	~	NA	Value $\geq 38.3^{\circ}$ C and $\geq 0.8^{\circ}$ C increase from baseline

The BMI will be computed similarly to description in [Section 5.3](#) at post-baseline visits using weight at visit and last available height measurement.

In addition, normal age and sex-based z-scores and percentiles for BMI will be determined using the WHO growth charts. Age and sex-based BMI categories include: Underweight (< 5 percentile), Normal ($\geq 5 - < 85$ percentile), Overweight ($\geq 85 - < 95$ percentile), Obese (≥ 95 percentile).

Descriptive statistics for weight, height, BMI, BMI World Health Organization adjusted z-scores and percentile will be provided. The categorical variables of BMI categories will be tabulated for each category as mentioned above. Data will be listed.

8.8. Electrocardiography

A 12-lead ECG will be recorded at the time points detailed in Table 3 of the study protocol. All ECGs will be performed after at least 5 minutes rest in a supine or semi-supine position. A qualified physician at a central diagnostic center will be interpreting the ECG. A central ECG Standard 12-lead ECG will record heart rate (HR), PR interval (Time from the beginning of the P wave to the beginning of the QRS complex in electrocardiogram), RR interval (Time between the start of one R wave and the start of the next R wave in the ECG), QT interval, Fridericia's corrected QT interval (QTcF), and QRS duration (Graphical deflections corresponding to ventricular depolarization in a typical electrocardiogram).

All ECG results outside of the reference ranges will be judged by the investigator as belonging to one of the following categories:

- abnormal and not clinically significant
- abnormal and clinically significant

If an abnormal post-baseline QTcF value >500 msec or change from screening >60 msec is found, the investigator must further evaluate QTcF based on protocol section 7.8.

Shifts (normal and abnormal) from baseline to overall result interpretation, each visit and last assessment, will be summarized using patient counts for the centrally-read interpretation. For overall result interpretation the worst post-baseline finding for the patient (the abnormal finding if there are both normal and abnormal findings) will be used in the summaries. Summary statistics for ECG variables values will be presented. Actual values and changes from baseline to each scheduled visit and last assessment will be summarized using descriptive statistics.

QTcF values will be classified as having QTc prolongation if any of the following conditions are met.

- Confirmed QTcF >450 msec
- Confirmed QTcF >480 msec
- Confirmed QTcF >500 msec
- Increase from screening QTcF > 60 msec
- Increase from screening confirmed QTcF > 60 msec

Screening is defined as the last non-missing ECG value prior to first dose IMP and the confirmed QTcF is defined as the average of up to 3 standard ECG values at a visit, or a single summary ECG. If there are more than 3 standard or more than one summary ECG at a visit, then use the last ECGs for the confirmed QTcF.

The number and percentage of patients with QTc prolongation will be summarized by treatment and overall, and by visit and last assessment.

The incidence of potentially clinically significant abnormal values for ECG variables will be summarized using descriptive statistics with the criteria presented in Table 7. The summary will be completed by treatment and overall, and age groups (6 to < 8 years, 8 to < 12 years, 12 to < 16 years, and ≥ 16 years), and overall using the age at screening.

Table 7: Potentially Clinically Significant Values for ECG Variables by Age

ECG parameter (unit)^a	Age (years old)	Potentially Clinically Significant Low	Potentially Clinically Significant High
HR (bpm)	6 to <8	< 65	> 115
	8 to <12	< 55	> 110
	12 to <16	< 50	> 105
	≥16	< 50	> 100
PR interval (msec)	6 to <8	--	> 160
	8 to <12	--	> 175
	12 to <16	--	> 180
	≥16	--	> 200
QRS interval (msec)	6 to <8	--	> 100
	8 to <12	--	> 105
	12 to <16	--	> 110
	≥16	--	> 120

^a bpm=beats per minute; HR=heart rate; PR interval =Time from the beginning of the P wave to the beginning of the QRS complex in electrocardiogram; RR interval =Time between the start of one R wave and the start of the next R wave in the ECG; QRS duration =Graphical deflections corresponding to ventricular depolarization in a typical electrocardiogram

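### SAP Section 8.8 pools five QTcF criteria into one QTc prolongation count, so the number of patients above 480 or 500 msec is never tabulated

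*SAP*

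**What the plan says.** SAP Section 8.8 defines a single class: "QTcF values will be classified as having QTc prolongation if any of the following conditions are met". Five conditions follow:

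- the lowest absolute level, given as "Confirmed QTcF >450 msec";
- two higher absolute levels, a confirmed value above 480 msec and one above 500 msec;
- a change criterion with no confirmation required, given as "Increase from screening QTcF > 60 msec";
- the same size of change with confirmation, given as "Increase from screening confirmed QTcF > 60 msec".

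The confirmed value is the mean of up to three standard ECGs at a visit, or one summary ECG. Screening is the last available ECG value before the first dose. One output follows: "The number and percentage of patients with QTc prolongation will be summarized by treatment and overall, and by visit and last assessment".

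Earlier in the section, two levels trigger further evaluation by the investigator: "If an abnormal post-baseline QTcF value >500 msec or change from screening >60 msec is found".

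**The concern.** A graded list of thresholds is useful because it separates borderline values from marked ones. Joining the thresholds by a logical OR and reporting one count removes that separation, because the lowest threshold absorbs the higher ones. Followed literally, the QTc table delivers less than the list above it promises. A reader of the study report could not learn from it how many patients in each arm exceeded 480 or 500 msec, or how many had an increase above 60 msec. The section itself treats two of these levels as distinct, since it ties investigator action to them.

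**Working it through.** There is no plan figure to reproduce; the check is one of set logic. All definitions come from SAP Section 8.8. Write m for the confirmed QTcF at a visit, r for the individual readings and s for the screening value. Number the conditions C1 (m > 450), C2 (m > 480), C3 (m > 500), C4 (increase > 60) and C5 (confirmed increase > 60).

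**Step 1: absolute thresholds.** m > 500 implies m > 480, which implies m > 450. Hence (C1 or C2 or C3) = C1. This needs no assumption. A patient at 501 msec meets C1, C2 and C3 and adds 1 to the count; a patient at 451 msec meets C1 only and also adds 1.

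**Step 2: change criteria.** Suppose C4 is met when any reading at the visit exceeds s by more than 60, and both criteria use the same s. A mean cannot exceed its maximum, so m − s > 60 implies max(r) − s > 60. C5 then implies C4, and the whole rule reduces to C1 or C4.

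This reduction was checked on 2,000,000 simulated visits with one to three readings each. The assumed distributions were a pre-dose mean of 400 (SD 25), a post-dose mean of 430 (SD 35) and a reading error SD of 12 msec. They serve only to test the logic and do not estimate rates in this trial. The five-condition rule flagged 770,341 visits, C1 or C4 flagged 770,341, and 0 visits differed.

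**Step 3: where Step 2 fails.** Each of its two premises can be dropped.

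- If C4 uses one selected reading, such as the last, then increases of 90, 50 and 50 msec have a mean of (90 + 50 + 50)/3 = 63.3 msec. C5 is met and C4 is not.
- If C5 is measured from an averaged screening value and C4 from the single last value, C5 can add patients. In a second simulated set of the same kind, 12,894 of 2,000,000 visits changed class.

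C2 and C3 remain redundant in both cases, because Step 1 does not depend on s or on the choice of reading.

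**Step 4: the two chains are separate.** In the first simulated set, 189,140 visits met C4 without C1 and 174,455 met C1 without C4. The five conditions therefore form two chains, absolute and change, and neither contains the other.

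**Step 5: other places that could supply the counts.**

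- Table 7 (potentially clinically significant ECG values) covers heart rate, PR and QRS. It has no QTcF row.
- The ECG shift table uses normal or abnormal from the central interpretation, with no msec threshold.
- The ECG descriptive statistics cover values and changes by visit and, under Section 4.1, include a maximum. This shows whether the summarized values passed a threshold in an arm, but not in how many patients.

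**Step 6: what a maximum leaves open.** Section 2.4 plans about 43 patients on TEV-50717 and 22 on placebo. One active patient above 500 msec is 1/43 = 2.3%; three are 3/43 = 7.0%. The same maximum is compatible with either.

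**The case against.** The strongest reply is that this is loose drafting. A ladder of 450, 480 and 500 msec has little purpose except as separate table rows, the classifying sentence speaks of values rather than patients, and the summary sentence does not say outright that the conditions are pooled. A programmer may well produce one row per condition. That intention is plausible, but the text gives an any-of rule for one named class and then one count of patients in it. If separate rows were meant, saying so costs nothing.

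Three stronger inferences are tempting, and the document does not support them.

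- **That all five conditions are nested, or that three are certainly inert.** There are two chains, and the redundancy of the confirmed increase rests on premises the SAP does not settle. It does not say which reading the unconfirmed criterion uses. Because the confirmed value is defined for a visit in general, the wording of the fifth condition could also mean an increase from an averaged screening value.
- **That marked prolongation is hidden.** The per-arm maximum can reveal an extreme value. What is lost is the number of patients.
- **That single noisy readings materially inflate the class.** Any such rate needs an assumed number of readings per visit. The SAP allows up to three standard ECGs or one summary ECG and does not say that triplicates are routine. With one reading per visit and the same screening value, the two change criteria coincide and the contrast disappears.

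**Conclusion.** The point stands in a limited form. As written, two of the five listed conditions (confirmed above 480 and above 500 msec) can never affect the only QTc prolongation count that is planned; this is a matter of logic and needs no assumption. A third, the confirmed increase above 60 msec, is also without effect if both change criteria share the single screening value and the unconfirmed one covers every reading at the visit. No display specified in Section 8.8 gives the number of patients above 480 or 500 msec, or the number with an increase above 60 msec as distinct from the composite. The consequence is confined to one descriptive safety table. No efficacy result is affected, and the maximum in the descriptive statistics remains as a partial safeguard.

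**What to change.** Replace the any-of composite in Section 8.8 by separate n (%) rows for each treatment group and overall, by visit and at last assessment:

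- confirmed QTcF above 450 msec
- confirmed QTcF above 480 msec
- confirmed QTcF above 500 msec
- increase from screening above 60 msec
- confirmed increase from screening above 60 msec

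State for each change criterion whether the screening value is the single last reading or an average. In the same edit, state which reading or readings the unconfirmed criterion uses. These are the plan's own thresholds, so no clinical rule changes. The cost is an edit to one paragraph and a few extra rows in one safety table, with no new data.

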4.4. Study Days and Visits

Study days will be numbered relative to the baseline visit date. Day 1 is defined as the date of the baseline visit, and the first dose of the IMP will be taken the next morning (day 2). Days will be numbered relative to baseline (ie, ..., -2, -1, 1, 2, ...; day -1 being the day before the baseline visit).

For efficacy and safety by-visit analyses, data collected at post-baseline scheduled visits will be included using their scheduled visit.

Data collected at early termination and unscheduled visits will be included and assigned to a visit window as described below.

Table 2: Visit Windows for Early Termination Visit for Efficacy Assessments

Assessment ^a	Study Day Window	Scheduled Day	Scheduled Visit/Week
MD-CRS	Day 2 - 73	Day 63	Week 9
	Day 74 - 94	Day 84	Week 12
	Day 95 - EOT	Day 105	Week 15
	≥Day after EOT	Day 112	Week 16
CaGI-I, CGI-S, PGI-I	Day 2 - 35	Day 21	Week 3
	Day 36 - 53	Day 49	Week 7
	Day 54 - 73	Day 63	Week 9
	Day 74 - 94	Day 84	Week 12
	Day 95 - EOT	Day 105	Week 15
	≥Day after EOT	Day 112	Week 16
CGI-I	Day 2 - 10	Day 7	Week 1
	Day 11 - 17	Day 14	Week 2
	Day 18 – 24	Day 21	Week 3
	Day 25 - 31	Day 28	Week 4
	Day 32 - 38	Day 35	Week 5
	Day 39 - 45	Day 42	Week 6
	Day 46 - 53	Day 49	Week 7
	Day 54 - 73	Day 63	Week 9
	Day 74 - 94	Day 84	Week 12
	Day 95 - EOT	Day 105	Week 15
	≥Day after EOT	Day 112	Week 16
PEDI-CAT, PedsQL	Day 2 – EOT	Day 105	Week 15

Assessment ^a	Study Day Window	Scheduled Day	Scheduled Visit/Week
UHDRS-TMS, UHDRS-TMC, UHDRS-TMD	Day 2 - 73	Day 63	Week 9
	Day 74 - 94	Day 84	Week 12
	≥Day 95 - EOT	Day 105	Week 15

^a CaGI-I=Caregiver Global Impression of Improvement; CGI-I=Clinical Global Impression of Improvement; CGI-S=Clinical Global Impression of Severity; PGI-I=Patient Global Impression of Improvement; UHDRS-TMS=Unified Huntington’s Disease Rating Scale-Total Motor Score; UHDRS-TMC=Unified Huntington’s Disease Rating Scale-Total Maximal Chorea; UHDRS-TMD=Unified Huntington’s Disease Rating Scale-Total Maximal Dystonia; EOT=end of treatment

Table 3: Visit Windows for Early Termination Visit for Safety Assessments

Assessment ^a	Study Day Window	Scheduled day	Scheduled Visit/Week
Vital signs, Weight, C-SSRS, ESRS, CBCL- Syndrome Scale, ESS	Day 2 - 35	Day 21	Week 3
	Day 36 - 53	Day 49	Week 7
	Day 54 - 74	Day 63	Week 9
	Day 75 - 94	Day 84	Week 12
	Day 95 – EOT	Day 105	Week 15
	≥Day after EOT	Day 112	Week 16
ECG	Day 2 - 35	Day 21	Week 3
	Day 36 - 67	Day 49	Week 7
	Day 68 – EOT	Day 105	Week 15

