	≥Day after EOT	Day 112	Week 16
Laboratory tests other than pregnancy and drug screen	Day 2 – EOT	Day 105	Week 15
	≥Day after EOT	Day 112	Week 16
Orthostatic blood pressure, Physical exam, Neurological exam, height, CBCL-full assessment	Day 2 – EOT	Day 105	Week 15

^a CBCL=Child Behavior Checklist (for ages 6-18); C-SSRS=Columbia-Suicide Severity Rating Scale; ECG=electrocardiogram; ESRS=Extrapyramidal Symptom Rating Scale (subscales I and II); ESS =Epworth Sleepiness Scale (for children and adolescents); EOT=end of treatment

After mapping the data to the analysis visits of unscheduled and early termination visits, the following rules will apply unless other handling is specified for a particular analysis:

- If there is a scheduled visit in the analysis window, the last non- missing scheduled visit will be selected.
- If there is no scheduled visit, but early termination visit, early termination visit will be selected.

- If there are no scheduled or early termination visits, the record closest to the planned assessment day will be selected for analysis.
- If there are no scheduled or early termination visits, and 2 records are equidistant from the scheduled day, then the later record will be selected.
- If a patient has no scheduled record or early termination/unscheduled visits in an analysis window, the patient will be considered missing at that visit.

For these analyses performed by time period, eg, adverse events, the following definitions will be used:

- Titration Period - from the first dose of treatment until the day of the week 7 visit. For patients discontinued before the week 7, the Titration Period is until the later of the last dose of treatment and the early termination visit.
- Maintenance Period - from the day after the week 7 visit until the day of the week 15 visit. If a patient enters the Maintenance Period but discontinues treatment early, the Maintenance Period is until the later of the last dose of treatment and the early termination visit.
- Overall Treatment Period - includes the Titration and the Maintenance Periods, if applicable.
- Follow-up Period - from the end of the Overall Treatment Period through the end of the study.

For last assessment, the last available non-missing value will be used. Unscheduled visits that could not be mapped will not be displayed in the safety by-visit summaries, but they will be considered for the endpoint/last assessment visit.

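### QTc prolongation is counted only by visit and at last assessment, so the number of patients ever affected is never produced and some cases on unscheduled ECGs can fall out of every row

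*SAP*

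**What the plan says.** Section 8.8 lists five QTcF criteria: confirmed QTcF above 450, 480 and 500 msec, and an increase from screening of more than 60 msec, once unqualified and once for confirmed QTcF. The reporting rule is: "The number and percentage of patients with QTc prolongation will be summarized by treatment and overall, and by visit and last assessment".

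Which ECG represents a visit is settled in section 4.4. Unscheduled records are first mapped: "Data collected at early termination and unscheduled visits will be included and assigned to a visit window as described below". Then "the following rules will apply unless other handling is specified for a particular analysis", the first of them being: "If there is a scheduled visit in the analysis window, the last non- missing scheduled visit will be selected". Early termination records come next, and an unscheduled record is used only when neither exists. For the final row, "For last assessment, the last available non-missing value will be used".

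Two other passages show the plan using a fuller rule. Within 8.8, the normal/abnormal shift table has a worst-case entry: "For overall result interpretation the worst post-baseline finding for the patient" is used. For vital signs, section 8.7 says: "Summaries of potentially clinically significant abnormal values will include all post-baseline values (including scheduled, unscheduled, and withdrawal visits".

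**The concern.** The safety question for a QTc threshold is how many patients crossed it at any time on study drug. A table of visit-specific counts plus a last value does not answer that. A patient may cross the threshold on an ECG that the selection rules set aside, and the same patient may also appear at several visits. At stake is a descriptive safety result in a small trial, where a single patient changes the percentage visibly. The plan itself treats the upper thresholds as important, since section 8.8 requires further evaluation after QTcF above 500 msec or a change above 60 msec.

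**Working it through.** The SAP gives no expected number of QTc events or unscheduled ECGs, so there is no plan figure to reproduce. The check follows one ECG through the rules.

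**Inputs**
- ECG windows (4.4, Table 3): days 2–35 (week 3), 36–67 (week 7), 68–EOT (week 15), after EOT (week 16). With EOT at day 105 they last 34, 32 and 38 days on treatment. 34 + 32 + 38 = 104, which is every day from 2 to 105, so there is no gap.
- Arm sizes (2.4): about 43 and 22.
- Study drug stops at the week 15 visit, and patients return one week later (2.1).

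**1. Meaning of *overall* in the reporting rule.** Section 8.1 presents summaries by treatment group and for all patients. Section 8.8 (Table 7 summary) and section 8.10 use the same by-treatment-and-overall wording. It most naturally means an all-patients column, not an any-time count.

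**2. Trace, taking *visit* as the clinic visit.**
- An unscheduled ECG on day 60 maps to week 7. If the scheduled week 7 ECG is non-missing, that one is selected.
- An unscheduled ECG on day 80 maps to week 15. If the scheduled week 15 ECG is non-missing, that one is selected.
- In both cases the last assessment is the week 15 or week 16 ECG. If the selected ECGs are not prolonged, the patient is in no QTc row. For completers with a week 16 ECG, the last assessment is also off drug.

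**3. When the unscheduled ECG is still counted.** It is counted if its window has no scheduled or early termination ECG and it is closest to the planned day, or if it is the patient's last ECG. Loss therefore needs two things together: a preferred record in the same window and a later ECG that is not prolonged.

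**4. Trace, taking *visit* as the analysis window.** Section 8.8 defines confirmed QTcF as the average of up to three standard ECGs at a visit, or a single summary ECG, with the last ones used if there are more. If that replaces the 4.4 selection:
- With summary ECGs, the day 60 record follows a scheduled ECG near day 49 and is used. The day 80 record precedes a scheduled ECG near day 105 and is still displaced.
- With one scheduled reading of 450 and one unscheduled reading of 500 + x msec, the average is (450 + 500 + x)/2 = 475 + x/2. This exceeds 480 only if x > 10, and exceeds 500 only if x > 50.
- The increase criterion not labelled confirmed is outside this definition, so the 4.4 selection still governs it.

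Omission is reduced on this reading but not removed.

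**5. By-visit counts do not add up to patients.** One case at each of weeks 3, 7 and 15 may be one, two or three patients: 1/43 = 2.3% up to 3/43 = 7.0%. This holds with no unscheduled ECG at all.

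**6. Other summaries.** The worst-finding shift would show such a patient as abnormal at most, with no QTcF threshold attached. For the remaining ECG summary, "The incidence of potentially clinically significant abnormal values for ECG variables will be summarized using descriptive statistics with the criteria presented in Table 7", and Table 7 covers heart rate, PR and QRS only. Neither gives the missing count.

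**The case against.** The strongest reply has four parts.

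*Most unscheduled ECGs might be caught anyway.* A reader might infer that any patient whose prolongation appears on an unscheduled ECG goes uncounted. The SAP does not support that; step 3 of the working gives the conditions under which the patient is counted. Nor should early termination ECGs be included in the claim. Section 2.1 describes only a telephone contact after the early termination visit, so that ECG is normally the last available value and enters the last-assessment row.

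*The confirmed-QTcF rule may be the exception that section 4.4 allows.* This stands as an ambiguity. The SAP does not say whether *visit* there is the clinic visit or the mapped window. Step 4 shows that cases can still be omitted on the second reading.

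*The signal is not wholly lost.* That is correct: the abnormal finding can reach the interpretation shift, and values above 500 msec or changes above 60 msec go to a protocol section that is not shown. Neither yields the number of patients meeting a QTcF criterion.

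*The size is assumed.* This also stands. The SAP gives no QTc event rate and no reason why unscheduled ECGs would be taken, so it cannot be said that they are the ones most likely to be abnormal. The absence of QTc from Table 7 is no defect in itself, because QTcF has its own criteria in 8.8; it only means that Table 7 does not fill the gap.

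**Conclusion.** The point holds in a limited form. Section 8.8 provides no any-time post-baseline count for the QTcF criteria, and the planned rows cannot be combined into one. Under section 4.4, an unscheduled on-treatment ECG meeting a criterion can be missing from every QTc row if its window also holds a non-missing scheduled ECG and a later ECG is not prolonged. This rests on reading *overall* as all patients. How often loss occurs depends further on what *visit* means in the confirmed-QTcF definition, but the lack of an any-time count does not.

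The number of cases affected is unknown. As illustration only, one patient is 1/43 = 2.3% of the TEV-50717 arm or 1/22 = 4.5% of the placebo arm. The tables are descriptive and the primary efficacy result is untouched. The change should nonetheless be made, because the any-time count is the natural headline for these criteria and section 8.7 already uses all post-baseline values for vital signs.

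**What to change.** In section 8.8:

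- Add an any-post-baseline row for each QTcF criterion. Count each patient once, at the worst post-baseline value or the worst increase from screening, using all scheduled, unscheduled and early termination ECGs, in line with section 8.7. Make this the headline incidence and keep the by-visit and last-assessment rows.
- State whether *visit* in the confirmed-QTcF definition is the clinic visit or the analysis window, so that the averaging and last-ECG rules have one meaning.

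The cost is two sentences in the SAP and one table row per criterion. No new data are needed, and patient management does not change.

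### The Table 7 incidence of abnormal ECG values (heart rate, PR, QRS) has no baseline condition and no post-baseline restriction, so pre-dose exceedances are counted together with new ones

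*SAP*

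**What the plan says.** For ECG, SAP section 8.8 states: "The incidence of potentially clinically significant abnormal values for ECG variables will be summarized using descriptive statistics with the criteria presented in Table 7". Table 7 lists fixed limits by age for heart rate, PR and QRS, for example "HR (bpm) 6 to <8 < 65 > 115". No entry refers to baseline, and the text around the table does not say which visits feed the count.

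For vital signs, section 8.7 does both. It names the visits: "Summaries of potentially clinically significant abnormal values will include all post-baseline values (including scheduled, unscheduled, and withdrawal visits". Every non-orthostatic blood pressure and pulse criterion in Table 6 joins a limit to a change, for example "Value ≥ 135 and ≥ 15 increase from baseline" for a high pulse at ages 6-10 and "Value ≤ 50 and ≥ 15 decrease from baseline" for a low pulse at ages 11-18. The temperature criterion also has a change condition.

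Section 8.8 has three further ECG summaries that bear on the point:
- A shift table, based on the central reading: "Shifts (normal and abnormal) from baseline to overall result interpretation, each visit and last assessment, will be summarized using patient counts". Where a patient has several results on treatment, "the worst post-baseline finding for the patient (the abnormal finding if there are both normal and abnormal findings) will be used in the summaries".
- Descriptive statistics for actual values and changes from baseline of the ECG variables.
- Patient counts for QTcF, including an increase of more than 60 msec from the last ECG before the first dose.

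The investigator grades each out-of-range ECG as clinically significant or not. Section 8.8 assigns that grading to no table.

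**The concern.** A table of potentially clinically significant ECG values is read by comparing the arms. If values present before the first dose count the same as values that appear on treatment, part of any difference reflects who happened to enter with an abnormal ECG. With about 43 active and 22 placebo patients, a few such cases can produce an apparent difference or hide a real one, and the reader cannot tell which.

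The shift table does not resolve this for a given parameter. It classifies the whole ECG, so it cannot show whether a particular PR or QRS exceedance is new. A patient abnormal at baseline can also only stay abnormal or become normal, so deterioration in that patient does not register.

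**Working it through.** The SAP states no rate of ECG abnormality, so there is no figure to reproduce. The main check sets the rules side by side.

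| Feature | Vital signs (8.7, Table 6) | ECG heart rate, PR, QRS (8.8, Table 7) |
|---|---|---|
| Absolute limit | yes | yes |
| Change from baseline also required | yes, for all non-orthostatic criteria | no |
| Restricted to post-baseline values | yes, stated | not stated |

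**One patient through both tables.** Take a 13-year-old with a rate of 108 bpm before the first dose and 108 bpm on treatment.
- Table 7, 12 to <16 years, limit >105: 108 > 105, so the patient is counted.
- Table 6, 11-18 years, needs ≥120 and a rise of ≥15: 108 < 120 and the change is 108 − 108 = 0, so the patient is not counted.

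PR and QRS have no Table 6 counterpart. A PR past its limit before dosing and unchanged afterwards enters Table 7, and no other planned table shows for that patient that it was already there.

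**What the other ECG summaries can show.**
- The normal/abnormal shift separates normal-to-abnormal from abnormal-to-abnormal for the overall central interpretation. It does so neither by parameter nor by degree.
- Changes from baseline are group statistics and do not identify patients.
- The criterion of an increase above 60 msec identifies patients, but only for QTcF.

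**Illustration of size, under an assumed prevalence.** Inputs: planned group sizes of about 43 and 22 (SAP 2.4). Assumption: a proportion p in each arm is past a Table 7 limit before dosing and stays there, with no drug effect. Expected counts are 43p and 22p. The chance standard deviation of the arm difference is √[p(1−p)(1/43 + 1/22)], where 1/43 + 1/22 = 0.0687.

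| p | Active, 43p | Placebo, 22p | SD of difference (percentage points) |
|---|---|---|---|
| 0.05 | 2.1 | 1.1 | √(0.0475 × 0.0687) = 5.7 |
| 0.10 | 4.3 | 2.2 | √(0.09 × 0.0687) = 7.9 |
| 0.30 | 12.9 | 6.6 | √(0.21 × 0.0687) = 12.0 |

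An exact calculation with two independent binomials gives the probability of a difference of 10 percentage points or more, in either direction and by chance alone. It is 0.9% at p = 0.02, 6.7% at 0.05, 18.5% at 0.10 and 26.8% at 0.15.

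**The case against.** The strongest reply is that section 8.8 already contains baseline-relative ECG analyses. It plans a shift from baseline to the worst post-baseline central reading, changes from baseline for the ECG variables, and a QTcF increase criterion. A reader might infer from Table 7 that the ECG tables cannot separate new from pre-existing findings at all. The SAP does not support that, because the shift makes this separation for the overall interpretation.

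Heart rate is also partly covered. Table 6 applies a limit and a change of at least 15 bpm to pulse, and SAP Table 3 gives vital signs more visit windows (weeks 3, 7, 9, 12, 15 and 16) than ECG (weeks 3, 7, 15 and 16). The cover is partial because the limits and age bands differ.

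The word *incidence* need not mean new onset. Sections 5.5 and 5.6 use it for medical history and prior medication, where it can only be a patient count. Absolute limits for ECG and limit-plus-change for vital signs are also different choices and do not contradict each other. Both points stand: the SAP makes no false statement here. They do not help the reader of Table 7, who still sees old and new exceedances in one number.

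A reader might further infer that a move from a minor to a clinically significant ECG abnormality would go unseen in the report. That is not established. Adverse events are summarised and listed under 8.3, and whether such a change must be reported as one is not settled by the SAP.

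Finally, the prevalence is assumed. Eligibility rules outside the SAP could make it much lower, and full persistence is assumed as well.

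**Conclusion.** The point holds in a limited form. For heart rate, PR and QRS, the Table 7 count as written does not distinguish exceedances present before the first dose from new ones, and it is not confined to post-baseline values. The shift table cannot fill the gap by parameter, and it cannot show worsening among patients abnormal at baseline. With QTcF covered and heart rate partly covered, what remains is mainly PR and QRS.

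The conclusion rests on the text of 8.7 and 8.8 alone. The counts of about 4 of 43 and 2 of 22 at an assumed 10% (about 2 and 1 at 5%, about 13 and 7 at 30%) only illustrate why baseline status matters at this size. They do not predict what the trial will show. The tables are descriptive, no test or decision rule uses them, and the primary analysis is unaffected. This is a worthwhile reporting improvement of low severity.

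**What to change.** In section 8.8:

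1. State that the Table 7 summary counts post-baseline values, and say whether unscheduled and withdrawal visits are included, as 8.7 does.
2. Tabulate each Table 7 criterion by status on the last ECG before the first dose. Give patients newly meeting the criterion, with those not meeting it pre-dose as the denominator, and put patients already meeting it in a separate row.
3. Keep the two-level shift on the central reading. Add a separate baseline-to-worst table of the investigator's grading (not clinically significant, clinically significant). Do not merge the two into one scale, because they come from different raters.

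The new-onset count does not itself show further worsening in patients already past a limit. Item 3 is meant to help there.

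The cost is a few sentences and minor re-programming of descriptive tables from data already collected, with a slightly smaller denominator for the new-onset count. The pre-dose reference needs no new definition, since 8.8 already takes the last non-missing ECG before the first dose as its reference for QTcF.
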